6.0 Informed Consent Process

All participants will be given detailed oral and written information about the trial. Consent forms describing in detail the study intervention, study procedures and risks will be given to each participant and written documentation of informed consent is required prior to starting study medication/intervention. Participants must sign an informed consent document that has been approved by a participating centre's REB prior to any procedures being done specifically for the trial. Each participant should have sufficient opportunity to discuss the study and consider the information in the consent process prior to agreeing to participate. Participants may withdraw consent at any time during the course of the trial. The informed consent form will be signed and dated by the participant and the person who conducted the informed consent discussion. The original signed informed consent form will be retained in the participant's study files and a copy of the signed form will be provided to the participant.

7.0 Participant Confidentiality

All subject related information including Case Report Forms, evaluation forms, reports, etc. will be kept strictly confidential. All records will be kept in a secure, locked location and only research staff will have access to the records. Subjects will be identified only by means of a coded number specific to each subject. All computerized databases will identify subjects by numeric codes only, and will be password protected.

8.0 Data Management Responsibilities

Electronic data capture (REDCap: <http://project-redcap.org/>) will be used for this trial, meaning that all CRF data will be entered in electronic forms at the investigational site. Authorized study site personnel designated by the Investigator will complete data collection. Appropriate training and security measures will be completed with the Investigator and all authorized study site personnel prior to the study being initiated and any data being entered into the system for any study subjects. The study data will be housed on a secure in-house server and study documents will be retained for up to 25 years after completion of the study, or as required by Health Canada.

Appendix I: Schedule of Assessments

	Pre-study (routine clinical studies)	Baseline (Day 0)	Day 30 (± 1 week)	6 months (± 2 weeks)	12 months +/- 4 weeks (telephone)	24 month +/- 4 weeks (telephone)
Holter (optional)	X	Reports collected				
Echo (optional)	X	Reports collected				
Neuroimaging (CT or MRI)	X	Reports collected				
Vascular Imaging (CTA/MRA/doppler)	X	Reports collected				
ECG	X	Reports collected	X	X		
Informed consent, randomization		X				
Demographics		X				
Medical History		X			X	X
Vital signs		X*	X	X		
Antithrombotic and thrombolytic therapy		X	X	X	X	X
NIHSS		X				
CHA2DS2-VASc		X				
TIA/Stroke Subtype / Etiology (OCSS/TOAST)		X				
Modified Rankin		X		X		
EQ-5D		X		X		
Adverse event assessment		X	X	X	X	X
New stroke/TIA, cardiac events		X	X	X	X	X
Return monitor / compliance diary			X			

*Height and weight will be obtained at this visit only.

Appendix II: Oxfordshire Classification of Stroke Subtype

Oxfordshire Community Stroke Project Classification

TAC — Total Anterior Circulation Stroke

LAC — Lacunar Stroke

PAC — Partial Anterior Circulation Stroke

POC — Posterior Circulation Stroke

Code last letter as follows:

(S) — Syndrome: Indeterminate pathogenesis, prior to imaging (e.g., TACS)

(I) — Infarct (e.g., TACI)

(H) — Hemorrhage (e.g., TACH)

References

"How well does the Oxfordshire Community Stroke Project classification predict the site and size of the infarct on brain imaging?"
J Neurol Neurosurg Psychiatry 2000;68:558-562.

Appendix III: TOAST Classification for Etiological Stroke/TIA Diagnosis

For classification of the most likely cause of the index ischemic stroke or TIA event, the TOAST (Trial of ORG 10172 in Acute Stroke Treatment) criteria will be used. This classification should be completed by the enrolling study physician at baseline and at the 90-day follow-up.

The 5 major categories of the TOAST classification are as follows:

- large-artery atherosclerosis, including large-artery thrombosis and artery-to-artery embolism
- cardioembolism
- small-artery occlusion
- stroke of other determined cause
- stroke of undetermined cause.

For strokes of undetermined origin, 1 of 2 explanations is needed: (1) no cause was found despite an extensive evaluation or (2) a most likely cause could not be determined because more than 1 plausible cause was found.

The subtype definitions will be based on risk factor profiles, clinical features, and results of diagnostic tests. Diagnostic tests will include brain imaging, vascular imaging, ECG/Holter, and echocardiography.

Reference:

Appendix IV: Modified Rankin Scale

Modified Rankin Scale Structured Interview (MRSSI)

0 = No symptoms at all; no limitations and no symptoms.

1 = No significant disability; symptoms present but not other limitations. Question: Does the person have difficulty reading or writing, difficulty speaking or finding the right word, problems with balance or coordination, visual problems, numbness (face, arms, legs, hands, feet), loss of movement (face, arms, legs, hands, feet), difficulty with swallowing, or other symptom resulting from stroke?

2 = Slight disability; limitations in participation in usual social roles, but independent for ADL. Questions: Has there been a change in the person's ability to work or look after others if these were roles before stroke? Has there been a change in the person's ability to participate in previous social and leisure activities? Has the person had problems with relationships or become isolated?

3 = Moderate disability; need for assistance with some instrumental ADL but not basic ADL. Question: Is assistance essential for preparing a simple meal, doing household chores, looking after money, shopping, or traveling locally?

4 = Moderately severe disability; need for assistance with some basic ADL, but not requiring constant care. Question: Is assistance essential for eating, using the toilet, daily hygiene, or walking?

5 = Severe disability; someone needs to be available at all times; care may be provided by either a trained or an untrained caregiver. Question: Does the person require constant care?

References

*Wilson, L. J. T., Harendran, A., Grant, M., Baird, T., Schultz, U. G. R., Muir, K. W., Bone, I. (2002). Improving the assessment of outcomes in stroke: Use of a structured interview to assign grades on the Modified Rankin Scale. *Stroke*, 33, 2243-2246.

PER DIEM Device Rhythm Adjudication Process (Instructions for Cardiac Device Nurses)**Calgary Device Nurses****Designated Cardiologists**

[name]

[name]

Process

- 1.0 ILR Device nurse checks on PER DIEM Carelink Clinic for Alerts MWF
- 2.0 Sends an email message to the designated adjudicating MD using the Rhythm template in the body of the email. (copy and paste or as a template*)
- 3.0 The e-mail message should have a standard subject line: "Rhythm Adjudication: <Subject number> <Alert/transmission date (YY/MM/DD)>**"
- 4.0 Naming Convention will be for Calgary patients FMC-study number (delete clinic number 45 as this is misleading): For Edmonton patients GNH-study number (we need the site prefixes as the study numbers are randomized per site and not for the whole study)
- 5.0 The designated MD will have 2 business days to respond
- 6.0 If there is no response to the email, the ILR device nurse will send a reminder email
- 7.0 As soon as the response is received the ILR nurse will send report to the Study Coordinators with a copy to the PI ([name])

ILR Device Capabilities/Troubleshooting

1. Shortest duration of AF that Reveal LINQ can store is 2 minutes.
2. An "AF Alert" does not mean that the rhythm is definitely AF – this needs confirmed by a Cardiologist.
3. For PER DIEM the LINQ device is programmed to store AF Episodes with a duration of 2 minutes and longer. The nominal setting for Reason for Monitoring: Cryptogenic Stroke is "all episodes". Threshold Options are All Episodes, 6,10,20,60 minutes. For Cryptogenic stroke-use "all episodes".
4. When a patient is transferred from one clinic to another all of the device data is transferred. Care Alerts settings are not transferred from one clinic to another. They are set at the Root or Parent Clinic level. You can retrieve previous episodes by checking the episode tab.
5. The volume of Event Reports can be reduce by tailoring your Care Alerts to your patient population. You can reduce the duplication of episode review by marking the episode as reviewed under the Episode Tab.
6. If an Event Report for AF is received with "No Data Available" – please request that the patient send a manual transmission. This situation can occur with AF episodes <10 minutes in devices purchased prior to March 7, 2016.
7. You can reduce your false positives for under-sensing or over-sensing by reprogramming the LINQ device.

Please review the attached PDF file, indicate your responses below by marking with an "X" or highlighting the relevant answer and send your response within 2 business days of receipt to the sender.

1. Rhythm diagnosis (select one):

- No Atrial Fib/Aflutter
- Atrial Fib/Aflutter Possible
- Atrial Fib/Aflutter Definite/ High Probability

Identify event number(s) containing definite AF: _____

Duration of longest episode: _____

2. Other significant arrhythmia(s) (select all that apply):

- HR<40
- HR>140
- Sustained ventricular tachycardia / ventricular fibrillation
- Complete heart block
- Pause ≥5 s
- Other, describe: _____

Identify event number(s) containing significant arrhythmia: _____

3. Quality of ECG recording (select one):

- Excellent, atrial activity clearly visible or clearly absent
- Moderate, atrial activity not reliably seen but rhythm interpretation possible on basis of R-R intervals alone
- Poor, excessive noise, loss of contact

4. Request second reading by another cardiologist

- Yes
- No

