3.3 Study Enrollment Process

The study will be conducted over 24-30 months. A total of 300 patients will be recruited during from inpatient stroke units and stroke prevention clinics at the Foothills Medical Centre, University of Alberta Hospitals, and Grey Nuns Community Hospital using standard of care screening methods. Eligible patients will be randomized in a 1:1 ratio to receive either an ILR coupled with remote monitoring for 12 months versus an ELR for 30 days. A centralized web based randomization process will be used. Patients will be randomized in

small, variable block sizes. Both groups of patients will receive the best standard of care for secondary stroke prevention based on the Canadian best practices guidelines.(12)

Monitoring with ELR for 30 days

The ELR group will be fitted with a battery operated SpiderFlash-t (Sorin Group, USA) auto-triggered ELR and will be provided with a diary to track total hours worn per day and any clinical symptoms.

ILR with remote monitoring for 12 months

The ILR plus remote monitoring group will have a Health Canada approved Medtronic Reveal LINQ device surgically implanted. This is a miniaturized recorder about the size of a clip on a pen (44.8 mm x 7.2 mm x 4.0mm) (Figure 1a). It can be readily inserted in a procedure room with a very low risk of complications. It will be linked to a wireless (cellular) remote monitoring system (MyCareLink) (Figure 1b).

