5.0 STATISTICAL METHODS

Sample Size and Power Calculation

A total of 300 patients will be randomized in the pilot phase. This sample size reflects 8% inflation for cross over (2% with either strategy) and loss to follow-up (5% in each group). This sample size provides 85% power to assess a clear difference in rates of atrial arrhythmia (AF / atrial flutter) that results in initiation of additional anti-platelet or OAC therapy between the two strategies (two- sided alpha of 5%). This estimate is based on the following assumptions:

1. Equal allocation (1:1) to ELR for 30 days vs. ILR plus remote monitoring for 12 months.
2. 10% rate of AF / atrial flutter that results in initiation of additional anti-platelet or OAC therapy in the ELR and 20% rate of this endpoint in the ILR plus remote monitoring group.

This estimate was derived using the Two Independent Proportions (Null Case) Power Analysis estimation method (PASS 2012).

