6.1.3 Primary Efficacy Analysis

Two sample comparison of proportions or patients reaching the primary outcome at one year, unadjusted.

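### The protocol suggests allocation ran separately by site, but the planned comparisons of proportions are unadjusted and no analysis names site as a stratum: valid, slightly conservative, and cheap to align

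*Protocol*

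**What the plan says.** **Allocation.** Protocol 3.3 states: "A centralized web based randomization process will be used". It adds a 1:1 ratio and short blocks of varying length. It names no stratification factor.

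The only statement about site is step 4.0 of the PER DIEM Device Rhythm Adjudication Process, which follows Appendix IV of the protocol. In explaining how patients are to be labelled, it says "we need the site prefixes as the study numbers are randomized per site and not for the whole study". It gives two prefixes, FMC for Calgary and GNH for Edmonton. Protocol 3.3 lists three recruiting hospitals, and SAP 1.1 describes one site in Calgary and two in Edmonton (one tertiary, one community).

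**Analysis.** SAP 6.1.3 gives the primary analysis as: "Two sample comparison of proportions or patients reaching the primary outcome at one year, unadjusted". SAP 6.2 uses the same form for secondary outcomes and adds a time-to-event analysis without naming a test, model, covariate or stratum. SAP 5.0 also assigns the primary outcome to a time-to-event analysis, again without a method. Site is not mentioned in any analysis section.

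**The concern.** When arms are balanced within sites by design, variation between sites drops out of the difference between arms. A test that ignores site still counts that variation in its standard error. If site predicts the outcome, the standard error is too large and some power is lost.

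Site could plausibly predict the outcome here. Patients come from inpatient stroke units and prevention clinics, from tertiary and community hospitals, and with mixed stroke mechanisms. Under the endpoint as written in the SAP, an event also requires a treatment change under usual practice, which may vary locally. The endpoint in the 4.0r amendment removes that link, but case mix can still differ.

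What is at stake is efficiency and agreement between design and analysis. False-positive risk is not at stake.

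**Working it through.** **1. The plan's own power figure.** Inputs from protocol 5.0 (repeated in SAP 1.4): "A total of 300 patients will be randomized in the pilot phase", so n = 150 per arm; "10% rate of AF / atrial flutter that results in initiation of additional anti-platelet or OAC therapy in the ELR and 20% rate" for the ILR arm; "two- sided alpha of 5" percent; "This sample size provides 85% power to assess a clear difference in rates of atrial arrhythmia".

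Pooled two-proportion test, with p̄ = 0.15 and p̄(1−p̄) = 0.1275:
- Null SE = √(2 × 0.1275/150) = 0.04123
- Alternative SE = √((0.09 + 0.16)/150) = 0.04082
- z = (0.10 − 1.96 × 0.04123)/0.04082 = 0.470, so power = 68.1%

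The stated 85% does not reproduce. That is a separate and larger matter. It is shown here because about 68% is the base against which any gain from stratifying must be read.

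**2. Size of the unadjusted test when arms are balanced within site.** Let w_s be the share of patients at site s and p_s its event rate under the null.
- Variance the test uses is proportional to p̄(1−p̄).
- True variance is proportional to Σ w_s p_s(1−p_s), which is never larger.
- With R = true/used, true size = 2 × [1 − Φ(1.96/√R)].

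The documents give no site rates or site sizes. Those below are assumptions, centred on 15% (the mean of 10% and 20%), with exact 1:1 balance within site as the limit of short blocks.

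| Assumed sites and null rates | Σ w_s p_s(1−p_s) | R | True size at nominal 0.05 |
|---|---|---|---|
| 3 equal, 15/15/15% | 0.1275 | 1.000 | 0.0500 |
| 3 equal, 12/15/18% | (0.1056 + 0.1275 + 0.1476)/3 = 0.1269 | 0.995 | 0.0495 |
| 3 equal, 10/15/20% | (0.0900 + 0.1275 + 0.1600)/3 = 0.1258 | 0.987 | 0.0485 |
| 3 equal, 5/15/25% | (0.0475 + 0.1275 + 0.1875)/3 = 0.1208 | 0.948 | 0.0441 |
| 200 and 100, 11.7/21.7% | 0.1255 | 0.983 | 0.0480 |
| 200 and 100, 8.3/28.3% | 0.1184 | 0.930 | 0.0421 |

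Simulation with 200,000 replicates per scenario agrees to about 0.001. The site-stratified Cochran-Mantel-Haenszel (CMH) test has simulated size of 0.049 to 0.050 throughout.

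**3. Power for 10% against 20% overall.** Each arm's rate is scaled in proportion to the site pattern. Worked example for 5/15/25%: the ELR rates are 3.3/10/16.7% and the ILR rates 6.7/20/33.3%.
- Alternative SE = √((0.0870 + 0.1481)/150) = 0.03960
- Unadjusted: z = (0.10 − 1.96 × 0.04123)/0.03960 = 0.485, power 68.6%
- Stratified: null SE = √(2 × 0.1208/150) = 0.04014; z = (0.10 − 1.96 × 0.04014)/0.03960 = 0.539, power 70.5%

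Simulated power:

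| Site pattern | Unadjusted | Stratified (CMH) |
|---|---|---|
| 3 equal, no difference | 68.6% | 68.7% |
| 3 equal, 12/15/18% | 68.5% | 68.8% |
| 3 equal, 10/15/20% | 68.7% | 69.3% |
| 3 equal, 5/15/25% | 69.2% | 71.3% |
| 200 and 100, 11.7/21.7% | 68.8% | 69.6% |
| 200 and 100, 8.3/28.3% | 69.2% | 72.0% |

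**The case against.** **The evidence for per-site allocation is thin.** The sentence is a labelling note for device nurses. It speaks of study numbers and explains why a prefix is needed. It is not a randomisation specification, and the section that is one names no stratum. Loose wording about numbering is a possible alternative reading. This stands to the extent that a reader might infer that the documents establish site-stratified randomisation, and they do not. Still, it is their only statement on the matter, it contrasts site with the whole study explicitly, and nothing contradicts it.

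**The number of strata is unclear.** Two prefixes against three hospitals means the note, taken literally, points to two groups. This stands, and it is the reason for confirming the strata before writing them in. The size of the effect is similar under both layouts.

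**Not every comparison excludes site.** Only the comparisons of proportions are declared unadjusted. The time-to-event plan is silent on site, so a reader who infers that it rules out a site term goes beyond the text.

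**The effect is negligible under realistic differences.** The 5/15/25% pattern is a five-fold range between hospitals sharing the same eligibility criteria. At milder patterns the gain is under 1 point, and a prespecified unadjusted test is valid. This stands as to size. It is not an argument against stratifying, which loses nothing when sites do not differ.

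**Conclusion.** The point holds as a minor mismatch between the likely allocation scheme and the planned analysis. If allocation was by site and detection rates differ between sites, the unadjusted test is valid but slightly conservative. In three equal sites the loss is under 1 point of power for small to moderate differences and about 2 points at an extreme one. With two unequal groups it reaches nearly 3 points at the extreme. If sites do not differ, there is no effect. All site rates and sizes are assumptions, and the calculation takes near-exact balance within site.

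Two stronger conclusions are not supported. A reader might infer that ignoring site makes the primary test invalid or raises the false-positive rate, but the true size is at or below 0.05 in every case. A reader might also hope that stratifying would recover the planned power. It would not: 85% power for 10% against 20% needs 228 per arm, or 456 in total, and 456/0.92 = 496 when the plan's allowance ("8% inflation for cross over (2% with either strategy) and loss to follow-up (5% in each group") is applied as an 8% loss.

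**What to change.** 1. Confirm from the randomisation system whether sequences were separate by site, and whether there were two or three strata. State the answer in protocol 3.3.
2. In SAP 6.1.3 and 6.2, replace the unadjusted comparison with one stratified by randomising site: a Mantel-Haenszel risk difference with the Cochran-Mantel-Haenszel test. Keep the unadjusted comparison as a sensitivity analysis.
3. For the time-to-event analyses in SAP 5.0 and 6.2, name a site-stratified log-rank test and Cox model. This also fills the gap left by the unnamed method.
4. Settle the wording before outcomes are compared between arms.

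The cost is SAP wording, one statement in the protocol, and confirmation of each patient's randomising site. That last step is needed because the prefix convention puts both Edmonton hospitals under one code, and the instruction in which it appears concerns ILR alerts only. No additional patients or visits are needed.

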STATISTICAL ANALYSIS PLAN

Post-Embolic Rhythm Detection with Implantable versus External Monitoring (PER DIEM) Study

Feb 2019

Version 1.0

Trial Registration ClinicalTrials.gov Identifier: NCT02428140

Statistical Analysis Plan v1.0

Clarification Note:

The statistical analysis plan v1.0 (SAP) defines the primary outcome using the endpoint from the protocol version 4.0 (dated February 22, 2016). There was an additional amendment to the protocol on April 26, 2016, where the AF adjudication process was specified, and the primary endpoint was defined as **definite AF lasting 2 minutes or more, including atrial flutter**. Version 1.0 of the SAP incorrectly carried forward the primary endpoint based on the Feb 22, 2016 version 4.0 protocol rather than the updated definition of the primary endpoint as approved by the steering committee and amended to the protocol on April 26, 2016.

SIGNATURES OF APPROVAL

[name]., Principal Investigator
University of Alberta Hospital

March 1st, 2019

Date

[name]., Investigator
Director Stroke Unit, Foothills Medical Centre

1 Mar 2019

Date

TABLE OF CONTENTS

	Page
SIGNATURES OF APPROVAL.....	2
TABLE OF CONTENTS	3
LIST OF TABLES.....	4
LIST OF ABBREVIATIONS	5
1.0 INTRODUCTION.....	6
1.1 Background	6
1.2 Primary Objectives.....	6
1.3 Study Design	6
1.4 Sample Size Determination	7
Table 1. Schedule of Assessments.....	8
1.5 Blinding	9
1.6 Definitions.....	9
2.0 ANALYSIS POPULATIONS.....	10
2.1 Intent-to-Treat Population	10
2.2 Per Protocol (PP) Population.....	10
3.0 INTERIM ANALYSES.....	10
4.0 MISSING DATA AND DATA TRANSFORMATION	10
5.0 STATISTICAL METHODS	10
5.1 Protocol Deviations and Protocol Violations.....	11
5.2 Demographic and Baseline Characteristics.....	11
6.0 EFFICACY ANALYSIS.....	11
6.1.1 Primary Outcome	11
6.1.2 Statistical Hypothesis.....	12
6.1.3 Primary Efficacy Analysis.....	12
6.2 Secondary Efficacy Analyses.....	12

LIST OF TABLES

	Page
Table 1. Schedule of Assessments.....	8

LIST OF ABBREVIATIONS

AE	Adverse Event
AIS	Acute Ischemic Stroke
ANCOVA	Analysis of Covariance
CI	Confidence Interval
ECG	Electrocardiogram
EMS	Emergency Medical Services
e-CRF	Electronic Case Report Form
ICH	Intracerebral Hemorrhage
IQR	interquartile range
mRS	Modified Rankin Scale
NCCT	Non-contrast Computed Tomography Scan
NIHSS	National Institutes of Health Stroke Scale
PERDIEM	Post-Embolic Rhythm Detection with Implantable versus External Monitoring (PER DIEM) Study
PP	Per Protocol
SAE	Serious Adverse Event
SD	Standard Deviation

1.0 INTRODUCTION

This document provides the details of statistical analyses planned for the PERDIEM study. In addition, it discusses the statistical issues relevant to these analyses (e.g., sample data to be used and missing data).

